3.0 STUDY DESIGN

3.1 Phase I

Because of the well published safety profiles of both quinacrine and capecitabine, the Phase I portion of our study will aim to determine the tolerability of both agents in combinations when used at established clinical doses. Given that capecitabine is considered as standard treatment for mCRC, a full dose of 1000mg/m² orally bid of capecitabine will be administered with different doses of quinacrine. The maximum dose of quinacrine to be tested is 200 mg bid. The first patient in this study will be treated with 1000 mg/m² orally bid of capecitabine on days 1-14, and a starting dose of 100 mg orally daily of quinacrine on days 1-21 of a 21 day cycle (dose level -2 in table below). All patients will be evaluated for baseline toxicity. Toxicity will be evaluated according to the National Cancer Institute Common Toxicity Criteria (current version 4.0).

A modified version 4B of Simon's accelerated titration design (Figure 3) will be used in the Phase I portion of our study to limit the number of patients treated at potentially sub therapeutic doses [60]. In this design, a cohort has at least one patient treated at a dose level (designated as "i"). If no DLT is observed (i.e. no toxicity, T, >2) at cycle 1, another single-patient cohort is treated with the next higher dose level (i.e., "Add 1 to i"). On the other hand, if a DLT is observed in a single- patient cohort in the first cycle, an additional two patients are treated at the same dose level (i.e. Dose i 2 patients). If another instance of toxicity > grade 2 is observed, three additional patients will be treated at that dose level. If at most 2 of the 6 patients treated at a dose level experience a DLT, that dose level is identified as the MTD.

Dose Escalation		
	Dose *	
Dose Level	Quinacrine (mg)	Capecitabine (mg/m2)
Level -2	100, qd	1000 bid

Level -1	100, bid	1000 bid
Level 0	200, bid	1000 bid

Adopting the modified version 4B of Simon's accelerated titration design, it is possible that only three patients are enrolled in Phase I. This situation can occur in the event that the first patient that received dose level -2, the first patient that received dose level -1 and the first patient that received dose level 0 do not experience toxicity>2.

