*NA indicates that the action taken is the same regardless of whether there were patients previously treated at a higher dose

The MTD will be used at recommended phase 2 dose (RP2D) unless there are any safety concerns. Patients who needed a dose reduction after being treated with RP2D in phase I will receive the reduced dose in phase II.

For the purposes of quinacrine dose escalation, the dose-limiting toxicities (DLT) that will be taken into account include toxicity grade >2 hematological, GI/diarrhea, skin, LFT abnormality or otherwise unexpected grade 3 toxicity or higher, associated with the combination therapy. Quinacrine dose modifications will not be made in the event of toxicities that are primarily attributed to capecitabine; namely, > grade 2 alopecia and hand and foot syndrome (HFS). Patients experiencing DLT will be permitted to continue their treatment after a single step dose reduction.

Intra-patient dose escalation will occur only for patients experiencing Common Toxicity Criteria < grade 2 toxicity on a previous course. The intra-patient dose escalation for a patient in lower level dose cohort will be on hold until the highest dose cohort patient completes first cycle of therapy. For purposes of toxicity assessment, patient response to the initial dose received will be considered. Total time in therapy, however, will be adjudged to include the whole duration the patient received treatment, regardless of the doses received.

General concomitant medications, dose adjustment, drug warnings and supportive care guidelines, duration of therapy, duration of follow up, and criteria for removal from treatment, as described throughout the protocol will be applied to both Phase I and II.

The endpoint of the Phase I portion of this study will occur when the safety and tolerability of the quinacrine-capecitabine combination is evaluated. Based on our preclinical data and the history of use of both capecitabine and quinacrine, we expect that the following regimen will be safely tolerated by the majority of patients.

	Premedications;				Cycle
Agent	Precautions	Dose	Route	Schedule	Length
Quinacrine	After a meal with a	200 mg tablets	Orally:	Daily on	
	glass of water	Orally twice a	at least 8 hours	Days 1-21	
		day	between each		
			dose		
Capecitabine*	Within 30 minutes	1000 mg/m ²	Orally:	Daily on	21 days
	after a meal with	Orally twice a	at least 8 hours	Days 1-14	(3 weeks)
	water	day	between each		
			dose		

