6.1.5 Expectedness

An Expected Adverse Event is one where the specificity or severity is consistent with the current information available from the resources.

An Unexpected Adverse Event is one where the nature, severity, or frequency of the event is related to participation in the research is not consistent with either:

- 1. The known or foreseeable risk of adverse events associated with the procedures involved in the research that are described in (a) the protocol-related documents, such as the IRB-approved research protocol, any applicable investigator brochure, and the current IRB-approved informed consent document, and (b) other relevant sources of information, such as product labeling and package inserts: or
- 2. The expected natural progression of any underlying disease, disorder, or condition of the subject (s) experiencing the adverse event and the subjects(s) predisposing risk factor profile for the adverse event.

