7.2 Capecitabine

NSC#: 712807

Supplier: Commercially Available

Hematologic

Hematologic side effects including lymphopenia (58% to 94%), anemia (44% to 74%), neutropenia (16% to 22%), and thrombocytopenia (15% to 21%) have been reported. Cases of severe hypertriglyceridemia induced by capecitabine have also been reported.

Gastrointestinal

Gastrointestinal side effects including diarrhea (50%), nausea (44%), vomiting (26%), stomatitis (23%), abdominal pain (17%), constipation (9%), and dyspepsia (6%) have been reported. A case of capecitabine-induced pancreatitis has also been reported.

Dermatologic

Dermatologic side effects including hand and foot syndrome (35% to 45%), dermatitis (23% to 31%), nail disorder (4%), alopecia, erythematous rash, pruritus, eruptive multiple lentigo maligna-like lesions, radiation recall dermatitis, pyogenic granulomas, photoeruption, hyperpigmentation, inflammatory responses in actinic keratosis have been reported. A case of leopard-like vitiligo and a case of subacute cutaneous lupus erythematosus have also been reported.

Hepatic

Hepatic side effects including hyperbilirubinemia (34%) and hepatic failure have been reported.

General

General side effects including fatigue (34%), pyrexia (10%), and limb pain (4%) have been reported.

Metabolic

Metabolic side effects including anorexia (20%) and dehydration (5%) have been reported.

Nervous system

Nervous system side effects including paresthesia (12%), headache (7%), dizziness (5%), and insomnia (3%) have been reported. A case of cerebellar ataxia has also been reported.

Ocular

Ocular side effects including eye irritation (10%) and lacrimal duct stenosis have been reported.

Cardiovascular

Cardiovascular side effects including edema (6%) have been reported. Three cases of severe

angina-like chest pain possibly or probably related to Capecitabine treatment have been reported. One case of Capecitabine-induced coronary vasospasm has also been reported.

Musculoskeletal

Musculoskeletal side effects including myalgia (4%) have been reported.

Other

Other side effects including a case of tumor lysis syndrome have been reported.

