Quinacrine temporarily imparts a yellow color to the urine and skin; however the drug does not cause jaundice [55]. Patients should be counseled regarding urine discoloration and/or skin discoloration. Since quinacrine may precipitate severe attacks of psoriasis and may exacerbate porphyria, the drug should not be used in patients with these conditions unless the potential benefits justify the possible risks [55].

Hepatic

Long-term high dose use was occasionally associated with reversible hepatitis.

General

General side effects include mild transient headache, dizziness (33%).

Metabolic

Metabolic side effects including anorexia (20%) and dehydration (5%) have been reported.

Nervous system

Nervous system side effects including fast frequencies in EEG have been reported. High dose usage can rarely be associated with restlessness, vertigo, insomnia, nightmares, hyperirritability, psychosis and convulsion (0.1-0.4% reported).

Ocular

Only one retinotoxicity case has been reported. High dose use can be associated with hypersensitivity reaction as corneal edema, reported in 600mg daily dose.

Cardiovascular

No known cardiovascular side effects. Musculoskeletal No known musculoskeletal side effects.

Other

Quinacrine is an oxidizing agent and can cause methemoglobinemia or hemolytic anemia especially in patients with glucose-6-phosphate dehydrogenase (G6PD) deficiency [69]. It should be administered with caution to patients with glucose-6-phosphate dehydrogenase deficiency [55].

Toxicity: Although some adults have survived single quinacrine hydrochloride doses up to 25 g, a dose of 6.8 g has been fatal when given intraduodenally. Symptoms of acute quinacrine toxicity include CNS excitation with restlessness, insomnia, psychic stimulation, and seizures; GI disorders; vascular collapse with hypotension, shock, cardiac arrhythmias or arrest; and yellow skin pigmentation [55].

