11. STATISTICAL CONSIDERATIONS

11.1 Study Design/Endpoints

The study is designed as a combined Phase I/II interventional non-randomized single-center study of the safety and efficacy of quinacrine in combination with capecitabine in the treatment of patients with advanced stage colorectal adenocarcinoma.

The primary aims in Phase I are to describe toxicities/adverse reactions of quinacrine treatment in combination with capecitabine in patients with advanced CRC. Simon's accelerated titration 4B design is used to determine the dose for Phase II part of the trial. This trial design will be utilized given that quinacrine has been used in the clinic for many decades. We are not anticipating additional toxicity due to the combination with capecitabine. Total Phase I enrollment will be between 3 and 18.

Figure 3 charts the accelerated titration phase I design. It indicates that at each dose level one patient will be initially treated. If that patient's common toxicity criteria score, T, is at most 2 the next patient is dosed at the next higher level. If the patient's score exceeds 2, two more patients are treated at the same dose level. If these two patients' scores are both at most 2, the next patient is treated at the next higher dose level. If both patients have scores higher than 2, the dose is de-escalated one level. If only one of *Committee 2015 For Chase Career Carter® Office of Clinical Because. All rights rearrand*

the two has a score higher than 2, then 3 additional patients are treated at the current dose level. Finally, if at most 2 patients among the 6 at this dose level have scores higher than 2, this dose is declared the MTD. When the dose is de-escalated, the number of patients treated at the lower dose level is enlarged to 6 by adding 5, if escalation from it was made using only one patient, or by adding 3, if 3 patients have been previously treated with the lower dose. The table below lists the chance of dose escalation, pesc, in terms of the underlying chance that this dose will result in a score, T > 2. For example, if the chance that T will exceed 2 is 30% the chance of escalation is 85%. The table also lists the chance of de-escalation, pdesc, in the same way, and the chance that the MTD will be decided, pstay, on first entering a dose level. The chance that a dose level will be declared MTD when being reached by de-escalation, mtddsc, is listed directly below line listing p (T>2).

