	Chan	ce of e	scalatio	on, MT	D in pl	ace or (de-esca	lation		
pesc:	0.981	0.928	0.847	0.744	0.625	0.496	0.363	0.232	0.109	
pstay:	0.013	0.033	0.043	0.041	0.031	0.018	0.008	0.002	0.000	
pdesc:	0.006	0.039	0.110	0.215	0.344	0.486	0.629	0.766	0.891	
p(T>2)	: 0.100	0.200	0.300	0.400	0.500	0.600	0.700	0.800	0.900	
mtddes	c· 0 99	0 0 93	6 0 82	8 0 67	6 0 50	0 0 32	4 0 1 7	2 0.06	4 0.010)

mtddesc: 0.990 0.936 0.828 0.676 0.500 0.324 0.172 0.064 0.010 Chance of MTD on de-escalation

The primary efficacy endpoint for Phase II is the rate of response by RECIST (CR, PR, SD, PD). The null hypothesis to be tested is that the RP2D observed in Phase I is not efficacious. We will use the standard Simon's two-stage design with 80% power at alpha level 0.05. The response rate is assumed to be 5% for the standard treatment and 20% for quinacrine in combination with capecitabine. The Phase II portion will first enroll 10 patients. The trial will be stopped if no patient responds to treatment. Otherwise, 19 additional patients will be enrolled for a total of 29 patients. The drug will be declared to have sufficient response rate if 4 or more subjects respond to treatment.

The other primary end point for Phase II is time to tumor progression, which will be analyzed by the Kaplan and Meier method.

Toxicity endpoint: If ever 5 of the initial cohort of 10 patients experience DLTs, or if ever 8 of the 29 total evaluable phase II patients do, the trial will be halted for excess toxicity and either dose adjusted or terminated. If the true chance of DLT is 33.3% the trial will be halted in this way with power 80.5%. If the true toxicity is at most 15%, the chance of termination in error is at most 6.3%.

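### Section 3.1 carries two DLT rules that can classify the same event differently, and the Phase II halting rule does not say which it uses

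*Combined protocol and SAP*

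**What the plan says.** **Rule A, any toxicity above grade 2.** The escalation paragraph of 3.1 moves to the next level on this condition: "If no DLT is observed (i.e. no toxicity, T, >2) at cycle 1". Figure 3 works on the toxicity score T alone. So does 11.1: "If the patient's score exceeds 2, two more patients are treated at the same dose level". The operating-characteristics table in 11.1 is indexed on the probability that T exceeds 2.

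**Rule B, a list.** Later in 3.1, for the purposes of quinacrine dose escalation, the DLTs to be considered "include toxicity grade >2 hematological, GI/diarrhea, skin, LFT abnormality or otherwise unexpected grade 3 toxicity or higher, associated with the combination therapy". This brings in organ class, expectedness and attribution, none of which appears in Rule A.

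**Where the count is used.** The action chart in 3.1 is driven by the number of DLTs. With no DLT in the one patient treated at a level, the next level opens, or level 0 is declared the MTD (when no higher level has been tried). With one DLT, two more patients are treated. The Phase II halting rule in 11.1 stops at 5 DLTs in the first 10 patients or 8 in 29: "If the true chance of DLT is 33.3% the trial will be halted in this way with power 80.5" (per cent). It does not define a DLT.

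**Expectedness.** Section 6.1.5 states: "An Expected Adverse Event is one where the specificity or severity is consistent with the current information available from the resources". It also lets the severity or frequency of an event make it unexpected.

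**Listed effects outside the four classes.** Section 7.2, for capecitabine: "General side effects including fatigue (34%), pyrexia (10%), and limb pain (4%) have been reported". Section 7.3, for quinacrine: "High dose usage can rarely be associated with restlessness, vertigo, insomnia, nightmares, hyperirritability, psychosis and convulsion (0.1-0.4% reported"). Neither entry gives a grade.

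**The concern.** Take a patient with grade 3 fatigue in cycle 1, judged expected because fatigue is a listed effect. Rule A calls it a DLT. Rule B, read as a closed list, does not. The rules also part on attribution: a grade 3 event judged unrelated to the combination satisfies Rule A and fails Rule B.

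This design leaves little room for that. Each level can be cleared on one patient, 3.1 allows that Phase I may enrol only three, and level 0 can become the MTD on a single patient. One classification can therefore settle the dose taken into Phase II. There, the same term drives the only numerical toxicity stop, so its operating characteristics belong to whichever definition the team happens to apply.

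**Working it through.** **1. Reproduce the Phase I table.** Let p be the chance that a patient has a counted event. A level is cleared if the first patient has none, or if the first has one and the next two have none:

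pesc = (1 − p) + p(1 − p)²

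| p | pesc computed | pesc in 11.1 |
|---|---|---|
| 0.10 | 0.981 | 0.981 |
| 0.20 | 0.928 | 0.928 |
| 0.30 | 0.847 | 0.847 |

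The other rows of the table also reproduce, to within 0.0005. The arithmetic is right. The open question is which event p refers to.

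**2. Reproduce the Phase II halting rule.** With X10 and X19 the DLT counts in the first 10 and the next 19 patients:

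P(halt) = P(X10 ≥ 5) + Σ(x = 0 to 4) P(X10 = x) · P(X19 ≥ 8 − x)

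- At p = 1/3: 0.213 + 0.592 = 0.805 (stated 80.5%).
- At p = 0.15: 0.010 + 0.053 = 0.063 (stated 6.3%).

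**3. What one disputed event does in Phase I.** Suppose the first patient at a level has an event that counts under Rule A only.

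- Rule B, read narrowly: no DLT, so the level is cleared with probability 1.
- Rule A: two more patients are treated, and the level is cleared at that point with probability (1 − p)², where p is the DLT rate in those two. This is 0.81, 0.64 or 0.49 for p = 0.10, 0.20 or 0.30. Otherwise the level expands to six or the dose is reduced.

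**4. How often that could arise.** The documents give no rate for such events. Assume a rate q per patient. Over at most three first-in-level patients the chance of at least one is 1 − (1 − q)³:

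| q (assumed) | Chance of at least one |
|---|---|
| 1% | 3.0% |
| 5% | 14.3% |
| 10% | 27.1% |

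**5. Effect on the stated probabilities.** Assume that some percentage points of the grade 3 or higher rate go uncounted under Rule B. The values 1, 5 and 10 are assumptions.

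| Points uncounted | Halting, true rate 33.3% | pesc, true rate 30% |
|---|---|---|
| 0 | 80.5% | 0.847 |
| 1 | 77.2% | 0.856 |
| 5 | 61.1% | 0.891 |
| 10 | 36.8% | 0.928 |

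The halting column is the formula in step 2 at p = 0.323, 0.283 and 0.233. The last column is the formula in step 1 at p = 0.29, 0.25 and 0.20; for example, 0.75 + 0.25 × 0.75² = 0.891.

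**The case against.** **The list may be the operative text.** It is introduced as applying to quinacrine dose escalation, the chart counts DLTs, and the bare T>2 wording could be shorthand for grade. That is a fair reading, but the escalation paragraph expressly glosses a DLT as T>2, and nothing ranks one text above the other. Reading the list as open-ended does not settle matters either: if every grade 3 or higher event counted anyway, the word *unexpected* would do no work.

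**Neither example is shown to be expected at grade 3.** This stands. The listed fatigue and convulsion carry no grade, 7.3 ties convulsion to high-dose use and calls it rare, and 6.1.5 allows severity to make an event unexpected. Such an event might count under both rules. The disagreement is therefore possible rather than demonstrated, and it turns on an investigator's judgement of expectedness.

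**The larger illustrations lean high.** This also stands. Five or ten points out of 33.3 means that 15% to 30% of grade 3 or higher toxicity is uncounted, which nothing in the documents supports. The one-point row belongs beside them.

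**Other safeguards exist.** The table for all other toxicities in 5.1 manages the individual patient, serious events are reviewed in real time (12.1), and "The MTD will be used at recommended phase 2 dose (RP2D) unless there are any safety concerns". These protect patients. None of them sets the DLT count.

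**Stronger readings to resist.** A reader might connect convulsion with the corticosteroid warning in 3.3, note that 7.0 does not repeat it, and infer an unmanaged interaction. The documents do not support that: 3.1 applies drug warnings given anywhere in the protocol to both phases, and no section says the antiemetics in 5.1 include corticosteroids. A reader might also take the sentence on alopecia and hand-foot syndrome as removing those events from the DLT count. It only bars quinacrine dose changes for them, while skin toxicity above grade 2 is a named DLT class.

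**Conclusion.** The point holds as an inconsistency between two stated rules, and it should be corrected. The rules differ on expectedness and organ class, and separately on attribution. The consequence is concrete because a single patient can clear a level or fix the MTD, and because Phase II halting depends on the same undefined count.

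It would go too far to say that the 80.5%, the 6.3% or the table in 11.1 is wrong. All reproduce, and each is correct for whatever event p is taken to mean. It would also go too far to say that halting power is 61.1% or 36.8%. Those figures, like 77.2%, rest on assumed uncounted shares and show direction and sensitivity only. The actual size cannot be determined from the documents.

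**What to change.** In 3.1, state one DLT definition and apply it to the escalation chart, Figure 3, 11.1 and the Phase II halting rule. A workable form is: *any grade 3 or higher toxicity associated with the combination, whether or not expected*. Then:

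- delete the qualifier *otherwise unexpected* from the list;
- replace the bare T>2 wording in 3.1, Figure 3 and 11.1 with the defined DLT term;
- label the table in 11.1 as indexed on the chance of a DLT (its entries do not change);
- say explicitly whether alopecia and hand-foot syndrome above grade 2, when attributed to capecitabine, count as DLTs.

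This wording is wider than the present list on expectedness and narrower than bare T>2 on attribution, so the sponsor should adopt it as a deliberate choice.

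The cost is a short text amendment. Adverse events are already recorded with grade, attribution and expectedness, so no new data are needed. The downside is that a Phase I level may expand by two patients after an event that the narrow list would have ignored, and Phase II may reach its halting limit sooner than under that list.

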3.2 Phase II

An open label, single stage design will be used in the Phase II portion of this study. The treatment outlined in the previous section, using RP2D derived from Phase I, will be administered on an outpatient basis. The patient will be requested to maintain a medication diary of each dose of medication. The medication diary will be returned to clinic staff at the end of each cycle. Reported adverse events and

potential risks of quinacrine and capecitabine are described in Section 6. Appropriate dose modifications for quinacrine and capecitabine are described in Section 5. No investigational or commercial agents or therapies other than those described below may be administered with the intent to treat the patient's malignancy.

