The chart below presents the different scenarios that can occur at a particular dose level, given the number of patients treated and number of patients that experience DLT, and the actions to be taken in the phase I dose escalation part of this study. The chart, therefore, is another means of understanding the research design of the Phase I portion of this study. Based on the research design, either 1, 3 or 6 patients can be treated with a particular dose level. The action will be either to escalate to the next dose with a single patient, add new patients to the current dose level (either 2, 3 or 5), de-escalate to the next lower dose level, declare the current dose level the MTD, or finally, declare all dose levels too toxic. For example, suppose dose level -2 does not result in a DLT, then dose level -1 is given to the next patient. If the patient treated with dose level -1 has a DLT, two more patients are treated with dose level -1. If all three patients treated with dose level -1 have DLTs, the study will be continued with the reduced dose, dose level -2. Because one patient was already treated at dose level -1, 5 more patients will be treated at dose level -2. If at most 2 of the six patients treated with dose level -2 have DLTs, dose level -2 will be declared MTD.

Number of	Numb	Were there patients	Action required
patients	er of	previously treated	
treated at	DLT's	at higher dose	
dose level		level? (Y/N)	
1	0	N	If level<0, escalate and treat 1 patient on higher dose level.
			If level = 0 , declare level 0 as MTD
		Y	Treat 5 more patients with this dose level
1	1	NA*	Treat 2 more patients with this dose level
3	1	Ν	If level<0, escalate and treat 1 patient on higher dose level.
			If level = 0 , declare level 0 as MTD
		Y	Treat 3 more patients with this dose level
3	2	NA	Treat 3 more patients with this dose level
3	3	NA	Reduce dose to next lower dose level. Continue study, taking
			note of the total number of patients treated with the lower
			dose level and number of DLT's and taking corresponding
			action required.
			If current dose level is -2, terminate study for excess toxicity
6	1 or 2	NA	Declare this dose the MTD
6	3 or		Reduce dose to next lower dose level. Continue study, taking
	more		note of the total number of patients treated with the lower
			dose level and number of DLT's and taking corresponding
			action required.
			If current dose level is -2, terminate study for excess toxicity

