10. MEASUREMENT OF ANTITUMOR EFFECT

Page 32 of 50

For the purposes of this study, patients should be re-evaluated for response after every 3 cycles. In addition to a baseline scan, confirmatory scans should also be obtained 6 weeks following initial documentation of objective response.

Response and progression will be evaluated in this study using the revised Response Evaluation Criteria in Solid Tumors (RECIST) guideline (version 1.1). Changes in the largest diameter (unidimensional measurement) of the tumor lesions and the shortest diameter in the case of malignant lymph nodes are used in the RECIST criteria.

Definitions

Evaluable for toxicity: All patients will be evaluable for toxicity from the time of their first treatment with quinacrine in combination with capecitabine. During the course of treatment, patients will be evaluated according to the National Cancer Institute CTCAE (current version 4.0).

Evaluable for objective response: Only those patients who have measurable disease present at baseline, have received at least one cycle of therapy, and have had their disease re-evaluated will be considered evaluable for response. These patients will have their response classified according to the definitions stated below. (Note: Patients who exhibit objective disease progression prior to the end of cycle 1 will also be considered evaluable.)

Evaluable Non-Target Disease Response: Patients who have lesions present at baseline that are evaluable but do not meet the definitions of measurable disease, have received at least one cycle of therapy, and have had their disease re- evaluated will be considered evaluable for non-target disease. The response assessment is based on the presence, absence, or unequivocal progression of the lesions.

Disease Parameters

Measurable disease: Measurable lesions are defined as those that can be accurately measured in at least one dimension (longest diameter for non-nodal lesions and short axis for nodal lesions to be recorded) as >20 mm by chest x-ray, as >10 mm with CT scan, or >10 mm with calipers by clinical exam. All tumor measurements must be recorded in millimeters (or decimal fractions of centimeters). Note: Tumor lesions that are situated in a previously irradiated area might or might not be considered measurable. If the investigator thinks it appropriate to include them, the conditions under which such lesions should be considered must be defined in the protocol.

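### As written, a Phase I patient who missed much of cycle 1 and had no DLT still clears a quinacrine level: no minimum intake is set for DLT evaluability, and the medication diary is required only in Phase II

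*Combined protocol and SAP*

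**What the plan says.** All references are to the combined protocol and SAP.

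- **Intake record.** The diary is described once, in section 3.2 Phase II: "The patient will be requested to maintain a medication diary of each dose of medication". The next sentence adds: "The medication diary will be returned to clinic staff at the end of each cycle". Section 3.1 Phase I mentions no diary, capsule count or adherence check, and the section 9 calendar has no row for one.
- **Carry-over to Phase I.** Section 3.1 names what applies to both phases: "General concomitant medications, dose adjustment, drug warnings and supportive care guidelines, duration of therapy, duration of follow up, and criteria for removal from treatment". Neither the diary nor drug accountability is in that list.
- **Who counts.** Section 10: "All patients will be evaluable for toxicity from the time of their first treatment with quinacrine in combination with capecitabine". No minimum share of cycle 1 doses is set.
- **Who is replaced.** Section 11.2 (Patient Replacement) covers, for both phases, only patients lost to follow-up with no clinical or radiological evaluation at all.
- **What one patient decides.** Section 3.1: "If no DLT is observed (i.e. no toxicity, T, >2) at cycle 1, another single-patient cohort is treated with the next higher dose level". For a patient without a DLT at the top level, with nobody treated higher, the action chart reads: "If level = 0 , declare level 0 as MTD". The same section accepts that "it is possible that only three patients are enrolled in Phase I".

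**The concern.** The escalation rule reads the absence of a DLT in cycle 1 as evidence about the assigned dose. That holds only if the patient took roughly that dose. At level 0, cycle 1 calls for 2 × 21 = 42 quinacrine and 2 × 14 = 28 capecitabine administrations, all outside the clinic, and the protocol does not require any of them to be documented in Phase I.

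The counting rules matter more than the diary. Even with a diary, sections 10 and 11.2 would leave an under-dosed, DLT-free patient in the count, because no rule uses what the diary shows. The two gaps together allow a level to be cleared, or level 0 to be declared the MTD, by a patient who did not really test it. Section 3.1 then makes the MTD the recommended Phase II dose unless there are safety concerns.

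**Working it through.** **1. Reproduce the plan's figures.** Section 11.1 describes the escalation rule in words and tabulates its properties. Let p be the chance of T > 2. A level is escalated if the first patient has no DLT, or if the first has one and the next two have none:

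pesc = (1 − p) + p(1 − p)²

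At p = 0.30: 0.700 + 0.30 × 0.49 = 0.700 + 0.147 = 0.847, the plan's table entry (its text says 85%). The companion entries also follow:

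- pstay = 2p²(1 − p) × (1 − p)³ = 0.126 × 0.343 = 0.043
- pdesc = p³ + 2p²(1 − p)[1 − (1 − p)³] = 0.027 + 0.126 × 0.657 = 0.110

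The whole table, p = 0.1 to 0.9, reproduces to three decimals. It assumes that every counted patient carries the level's full DLT risk.

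**2. How much rests on one patient.** At p = 0.30, the share of escalations decided by a single DLT-free patient is 0.700 / 0.847 = 82.6%. Across p = 0.1 to 0.9 it runs from 80% to 92%.

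**3. Illustrate under-dosing.** These assumptions are not in the documents: a share m of patients is under-dosed, and their DLT risk is k × p. The average risk becomes p_eff = p(1 − m) + m·k·p. With m = 20% and k = 0.5, p_eff = 0.9p.

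| True p | p_eff | pesc as stated | pesc with under-dosing |
|---|---|---|---|
| 0.10 | 0.09 | 0.981 | 0.910 + 0.09 × 0.8281 = 0.985 |
| 0.20 | 0.18 | 0.928 | 0.820 + 0.18 × 0.6724 = 0.941 |
| 0.30 | 0.27 | 0.847 | 0.730 + 0.27 × 0.5329 = 0.874 |
| 0.40 | 0.36 | 0.744 | 0.640 + 0.36 × 0.4096 = 0.787 |
| 0.50 | 0.45 | 0.625 | 0.550 + 0.45 × 0.3025 = 0.686 |

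Range for m = 10% to 30% and k = 0.5 down to 0: pesc is 0.861 to 0.921 at p = 0.30, 0.766 to 0.865 at p = 0.40, and 0.656 to 0.798 at p = 0.50.

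**4. Given that the first patient is the under-dosed one** (risk halved, later patients fully dosed), pesc = (1 − p/2) + (p/2)(1 − p)². At p = 0.30 this is 0.85 + 0.15 × 0.49, about 0.92. At p = 0.50 it is 0.75 + 0.25 × 0.25, about 0.81.

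**5. Could another record correct the decision in time?**

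- Section 6.2.1 records action on study drug as a detail of an adverse event, so a DLT-free patient who skipped doses may leave no entry.
- Section 7.1 hands out quinacrine each cycle and states no return or count.
- Appendix A has PK samples analysed together once the study is over, which is too late for escalation.

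**The case against.** Several points on the other side have force.

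- **Drafting slip.** The same section 3.2 paragraph holds plainly general text, such as the pointers to sections 5 and 6 and the bar on other anticancer treatment. The diary may have been meant for both phases. That stands as an explanation, but sites follow the text, and moving the sentence would not settle who counts as DLT-free.
- **Silence is not absence.** A reader might infer that Phase I intake goes unrecorded while Phase II intake is fully captured. The documents support neither half. They do not require a Phase I record, but a site may keep one, and in Phase II patients are only asked to keep a diary.
- **The diary's placement as sole cause.** A reader might also infer that the heading over the diary is what lets an under-dosed patient count. It is not: that follows from sections 10 and 11.2, and a Phase I diary alone would change no decision.
- **Other traces of exposure.** PK is planned in both phases, with pre-dose samples on day 1 of cycles 2 and 3. These could show gross under-dosing afterwards, although how much depends on the quinacrine half-life, given as 5–14 days in section 1.4 and 4 hours in section 8.1.1. Section 1.5 offers yellow skin as a sign of adequate dosing, but ties it to equilibrium, which section 1.4 places by the fourth week and cycle 1 may not reach. Neither is a check that can be relied on at the escalation decision.
- **Small effect at low toxicity.** Under the 20% assumption the rise is less than half a point at p = 0.10 and 1.3 points at p = 0.20. This stands.
- **Phase II backstop.** Section 11.1 halts at 5 DLTs in the first 10 patients or 8 in 29. This limits the harm, but only after patients have been treated at the dose in question.

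**Conclusion.** The point holds as a gap in the counting rules, made worse by the diary's location. As written, a Phase I patient who took clearly less than the assigned cycle 1 doses and had no DLT clears a level, or makes level 0 the MTD, on a single observation. No required record would show this before the decision.

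That conclusion rests on the text alone. The size does not: with 20% of patients under-dosed and their DLT risk halved, the chance of escalating rises by about 3 points at p = 0.30 (0.847 to 0.874), 4 at p = 0.40 (0.744 to 0.787) and 6 at p = 0.50 (0.625 to 0.686). The 20% and the halving are assumptions, and the effect is smaller where true toxicity is low. The documents do not show that under-dosing will be common or that the MTD will be wrong. This is an inexpensive improvement that should be made.

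**What to change.** 1. State that the diary and its return apply to Phase I and Phase II, add a calendar row, and require review at the end of cycle 1 before the next patient is dosed or the MTD is declared.
2. Amend sections 10 and 11.2 so that a Phase I patient counts as DLT-free for escalation only if a minimum share of cycle 1 doses, prespecified by the sponsor, was taken. Always count a patient who has a DLT, and do not treat doses held for toxicity as missed.
3. Replace Phase I patients who are not DLT-evaluable, and keep them in the safety tabulations.

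**Operating characteristics.** Because DLTs always count, the rule errs slightly towards caution. With m = 20%, k = 0.5 and p = 0.30, a counted patient has a DLT with chance (0.24 + 0.03) / (0.24 + 0.03 + 0.56) = 0.27 / 0.83 = 0.325. Then pesc = 0.675 + 0.325 × 0.675² = 0.823, against the stated 0.847.

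**Cost.** The diary is already planned for Phase II. Replacements rise with non-adherence. At 20%, the expected number is at most 3/0.8 − 3 = 0.75 for the smallest Phase I (3 patients) and 18/0.8 − 18 = 4.5 for the largest (18). It would be lower in practice, since under-dosed patients with a DLT are kept. A short delay before some escalations is possible.
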